10.1 Disposition of Participants and Discontinuations

The following will be presented in a summary table:

- Total number of participants screened (i.e., participants who gave informed consent)
- Number of screened participants who discontinued from the trial prior to study intervention overall and grouped by the main reason for discontinuation:
 - Participant did not meet all eligibility criteria
 - Withdrew consent
 - Other
- Number of treated participants
- Number and percentage of treated participants who completed study
- Number and percentage of treated participants who discontinued the study, with the primary reason of discontinuation by treatment and overall:
 - Adverse event
 - Lost to follow-up
 - Protocol non-compliance
 - Death
 - Withdrawal by subject
 - Other

A listing of discontinued participants will be provided.

10.2 Protocol Deviations / Exclusion from Analysis Sets

10.2.1 Important Protocol Deviations

Listings of important protocol deviations will be provided including the date and relative day in relation to dosing.

Important protocol deviations (IPDs) are protocol deviations that might significantly affect the completeness, accuracy, and/or reliability of the study data or that might significantly affect a participant's rights, safety, or well-being.

Important protocol deviations include:

- Participants enrolled and dosed on the study who did not satisfy enrolment criteria
- Participants that develop withdrawal criteria whilst on the study but are not withdrawn
- Participants that receive an incorrect dose
- Participants that receive an excluded concomitant medication

- Failure to collect data necessary to interpret primary endpoints
- Failure to collect necessary key safety data
- Deviation from Good Clinical Practice (GCP)
- Any other protocol deviation that might significantly affect the completeness, accuracy, and/or reliability of the study data or that might significantly affect a participant's rights, safety, or well-being.

Important protocol deviations will be identified for all participants by either site monitoring, medical review processes or programming and confirmed prior to or at the Data Review Meeting at the latest.

Any important protocol deviation is documented in SDTM datasets whether identified through site monitoring, medical review or programming. The management of protocol deviations is outside of this IAP document.

Clinically important protocol deviations (CIPDs) are a subset of important protocol deviations that could impact the key objectives of the study and that would lead to the exclusion of a participant from an analysis set (see Section 8.1 Definition of Analysis Sets).

CIPDs may be identified during the course of the study but will not require amendments to this IAP.

Important protocol deviations or important events that might have an effect on PK include, but may not be limited to the following:

- Adverse events, diarrhea etc. (these instances will be discussed on a case-by case basis)
- Vomiting after administration following oral dosing (these instances will be discussed in alignment with applicable regulatory guidelines on a case-by case basis)
- Sample processing errors that may lead to inaccurate bioanalytical results
- Inaccurate dosing or dosing errors (e.g. dose administration delayed, dose change or missed doses)
- Pre-dose sample collected after the actual start of dosing
- Incomplete meal consumption prior to dosing
- Concomitant medication violations

Should one or more of these events be available at the Data Review Meeting, its implication for PK evaluation will be discussed and agreed amongst relevant study team members (e.g. Sponsor Clinical Pharmacology/Biostatistics/Clinical Pharmacokinetics & Pharmacodynamics team representative). Appropriate action will be taken such as flagging individual values to be excluded from analysis.

10.2.2 Reasons Leading to the Exclusion from an Analysis Set

If participants are excluded from the PK Analysis Set, the reasons for exclusion will be listed.

A frequency table organized according to reason for exclusion from the PK Analysis Set, as well as a listing, will be provided.

11 Demographics and Other Baseline Characteristics

Demographics and baseline characteristics will be presented for the Safety Analysis Set.

11.1 Demographics

Descriptive statistics will be presented for age, height, weight, and body mass index (BMI). Frequency counts and percentages will be presented for sex, race, and ethnicity. The summary will be performed by ethnic group and overall.

Specifications for computation:

$$\text{BMI [kg/m}^2\text{]} = \frac{\text{weight [kg]}}{\text{height[cm]}^2} \times 10000$$

11.2 Medical History

Medical history will be coded using the Medical Dictionary for Regulatory Activities (MedDRA), Version 25.0 or higher, and listed.

11.3 Other Baseline Characteristics

Other baseline measurements, such as serology, alcohol and drugs of abuse screen, pregnancy test and follicle-stimulating hormone assessment in women, will be listed.

Baseline characteristics with respect to vital signs, physical examinations, and hematology/biochemistry will be part of Section 15 (Safety Evaluation).

12 Previous or Concomitant Therapies/Procedures

Medications will be presented for the Safety Analysis Set.

Previous medications are defined as any medication discontinued prior to the administration of study intervention. Concomitant medications are defined as any medication taken during the course of the study, with a starting date greater than or equal to the administration of study intervention, or with a starting date prior to the administration of study intervention and ongoing at the time of the administration of study intervention.

The World Health Organization Drug dictionary (WHO-DD), Version Global Mar2022 B3 or higher, will be used for coding of previous and concomitant medications and they will be described using Preferred Term (PT) as applicable.

Previous and concomitant medications will be listed. Concomitant procedures, if any, will also be listed.

13 Study Intervention: Compliance and Exposure

Exposure to study intervention will be recorded in the eCRF. The listing of exposure to the study intervention will include the treatment, ethnic group, dose, study intervention administered and date/time of administration.

14 Efficacy Analyses

Not applicable.

15 Safety Analyses

This section includes specifications for summarizing safety endpoints that are common across clinical studies such as adverse events, laboratory tests and vital signs.

All safety analyses will be performed for the Safety Analysis Set and will be presented by ethnic group. An additional column for all ethnic groups (overall) may be presented when specified.

15.1 Adverse Events

All AEs recorded during the course of the study will be coded with the MedDRA, Version 25.0 or higher, and assigned to a SOC and a PT.

Treatment-emergent AEs (TEAEs) are those events with onset dates on or after the administration of study intervention. Any AE occurring before the administration of study intervention on Day 1 and resolved before administration of study intervention or not worsening after administration of study intervention will be included in the AE listings but will not be included in the summary tables (unless otherwise stated). These will be referred to as “pre-treatment” AEs.

An AE of special interest (AESI) is a noteworthy event of the particular study treatments that can be appropriate to monitor closely. AESIs are noted in the CRF.

In case AE-related dates are partial, the available information will be used in a conservative approach to determine whether the AE is treatment-emergent.

All analyses described in this section will be based on TEAEs if not otherwise specified.

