#### 8.3 Adverse Events, Serious Adverse Events, and Other Safety Reporting

- The definitions of an AE and SAE are in [Appendix 4](#).
- The Investigator and any qualified designees (e.g., Subinvestigators) are responsible for detecting, documenting, and recording events that meet the definition of an AE or SAE. The Investigator remains responsible for following up AEs that are serious, considered related to the study intervention or study procedures, or that caused the participant to discontinue the study intervention or study, as specified in [Section 8.3.2](#).
- Requests for follow-up will usually be made via the Sponsor or Clinical Research Organization-designated study team member, although in exceptional circumstances the global patient safety department may contact the Investigator directly to obtain further information or to discuss the event.
- The method of recording, evaluating, and assessing causality of AEs and SAEs and the procedures for completing and transmitting SAE reports are in [Appendix 4](#).

- All AEs and SAEs will be collected from the signing of the ICF until the follow-up phone call at the timepoints specified in the SoA ([Section 1.3](#)). Beyond this reporting period, any new unsolicited SAEs that the Investigator spontaneously reports to the Sponsor will be collected and processed.
- All SAEs will be recorded and reported to the Sponsor or designee immediately and under no circumstance will this exceed 24 hours, as indicated in [Appendix 4](#). The Investigator will submit any updated SAE data to the Sponsor within 24 hours of it being available using the same procedure that was used for the initial report.
- Investigators are not obligated to actively solicit information on AEs or SAEs after the end of study participation. However, if the Investigator learns of any SAE, including a death, at any time after a participant has been discharged from the study, and he/she considers the event to be reasonably related to the study intervention or study participation, the Investigator will promptly notify the Sponsor.

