### Follow-up of AEs and SAEs

- The Investigator will perform or arrange for the conduct of supplemental measurements and/or evaluations, as medically indicated or as requested by the Sponsor to elucidate the nature and/or causality of the AE or SAE, as fully as possible. This may include additional laboratory tests or investigations, histopathological examinations, or consultation with other health care professionals.
- New or updated information will be recorded in the originally completed CRF.
- The Investigator will submit any updated SAE data to the Sponsor within 24 hours of receipt of the information.

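### The TEAE definition in SAP 15.1 has no worsening clause, so an AE that starts before the dose and worsens after it is neither treatment-emergent nor pre-treatment and can miss the TEAE tables

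*SAP*

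**What the plan says.** SAP 15.1 defines the term in one sentence: "Treatment-emergent AEs (TEAEs) are those events with onset dates on or after the administration of study intervention". Onset relative to dosing is the only criterion in that sentence.

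The next sentence deals with events that began before the dose. It covers "Any AE occurring before the administration of study intervention on Day 1 and resolved before administration of study intervention or not worsening after administration". These are listed, kept out of the summary tables and labelled pre-treatment.

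The section then sets the default for the AE analyses: "All analyses described in this section will be based on TEAEs if not otherwise specified". SAP 15.1.1 accordingly specifies tables of TEAEs: an overview, then counts by SOC and PT, by grade and by relationship. For incomplete dates, SAP 15.1 adds: "In case AE-related dates are partial, the available information will be used in a conservative approach to determine whether the AE is treatment-emergent".

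The protocol supplies no alternative definition. Its Appendix 1 expands the abbreviation TEAE but does not define it. Protocol section 3 and SAP section 5 make the occurrence of TEAEs (incidence, frequency, intensity and causality) part of the secondary safety endpoint.

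**The concern.** The two sentences in SAP 15.1 do not meet. The second uses lack of worsening as a ground for keeping a pre-dose event out of the tables, which makes sense only if a worsened event is meant to stay in. The definition that decides what enters the tables gives that event no way in.

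Pre-dose events will be on file. Protocol 8.3 states: "All AEs and SAEs will be collected from the signing of the ICF until the follow-up phone call". Screening may start on Day -28, so an event can begin before the dose and still be present at dosing. If it then becomes more severe or more frequent, that change is safety information about the period after dosing, and the TEAE tables are where the secondary safety endpoint is reported.

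A programmer who codes the definition as written would leave the event out. One who codes the apparent intent of the second sentence would include it. The SAP does not say which to do.

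**Working it through.** The plan states no figure to reproduce. The check is to sort each type of AE through the two sentences of SAP 15.1 and the TEAE default.

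- **(a) Onset after the dose.** Meets the definition. TEAE, tabulated.
- **(b) Onset before the dose, resolved before the dose.** Does not meet the definition and is named in the second sentence. Pre-treatment, listed only.
- **(c) Onset before the dose, ongoing, not worsening after it.** Does not meet the definition and is named in the second sentence. Pre-treatment, listed only.
- **(d) Onset before the dose, worsening after it.** Does not meet the definition, because onset precedes administration. Is not pre-treatment either, because it neither resolved before dosing nor failed to worsen. Unassigned.

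Only (d) is a gap. With the analyses resting on TEAEs unless otherwise specified, and nothing specified for (d), the literal result is that (d) does not reach the tables in SAP 15.1.1.

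Outputs that do not depend on the TEAE flag are the AE listings, the death and SAE listings in SAP 15.2, and the laboratory, vital-sign and ECG summaries in SAP 15.3 to 15.5.

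**Size for one participant.** Inputs are the planned numbers in Protocol 9.2: 12 per group and 24 in total, with up to 4 more per group allowed, so at most 16 per group and 32 in total. The change in incidence is 1/n:

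- planned group: 1/12 = 8.3 percentage points
- planned total: 1/24 = 4.2 points
- largest group: 1/16 = 6.3 points
- largest total: 1/32 = 3.1 points

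Participants are counted once per row. The any-TEAE row therefore moves by this amount only if the participant has no other TEAE, and a PT row only if there is no other TEAE under that term. For scale, the most frequent event among earlier healthy participants was headache, 5/58 = 8.6% (Protocol 2.3).

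**The case against.** The best answer is that the intent is plain: making lack of worsening a condition for exclusion would be pointless unless worsened events were to be kept. Worsening may also generate its own record. Protocol Appendix 4 counts exacerbation of a preexisting condition, in frequency or intensity, as an AE, and a new record after the dose would carry a post-dose onset and qualify as a TEAE. Both points reduce the risk. Neither closes the gap, because the intent is not in the definition and no passage says that a worsened AE receives a new onset.

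Three stronger readings are tempting, and the documents do not support them.

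- *A worsened event disappears from all safety output.* Only the TEAE tables in SAP 15.1.1 are at risk; the outputs listed above are not. Even within the overview table, the AESI entry is not worded as a count of TEAEs.
- *The worsened event is bound to keep its pre-dose onset.* Protocol Appendix 4 says: "New or updated information will be recorded in the originally completed CRF". That does not mention onset dates or whether worsening opens a new record. Recording guidance is left to the CRF Completion and Monitoring Conventions, which are not part of these documents.
- *An event on the morning of Day 1 before the dose counts as treatment-emergent.* The second sentence of SAP 15.1 expressly covers events before administration on Day 1 and makes them pre-treatment if they resolved or did not worsen. The comparison in the definition is with administration, not with the calendar day, and dose time is recorded (Protocol 6.4, SAP section 13). What remains is a small ambiguity: the definition speaks of onset dates, and the documents do not state that AE onset time is collected. With dates alone, such an event cannot be placed before or after the dose. Nor would counting it attribute it to the drug, since causality is assessed separately.

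It is also fair to say that AEs ongoing at dosing should be uncommon: eligibility is rechecked on Day -1 and clinical status before administration. No hypothesis is tested.

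**Conclusion.** The point stands in a narrow form. Taken literally, SAP 15.1 leaves an AE that starts before the dose and worsens after it without a class, and so outside the TEAE tables that report the secondary safety endpoint. That conflicts with the adjacent sentence, so it is more than a missing detail.

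The likely effect is small. The figures of 8.3 points in a group and 4.2 points overall apply per affected participant. They assume 12 dosed per group, no other TEAE in that participant, and worsening that is not recorded as a separate AE with post-dose onset. The documents give no rate of AEs ongoing at dosing; the expectation that there will be few is an assumption based on the healthy population. The pharmacokinetic analyses are not touched.

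**What to change.** Amend the TEAE sentence in SAP 15.1 to cover events with onset on or after administration of study intervention, or with onset before administration and worsening (in severity or frequency) after administration. Naming frequency as well as severity keeps the rule in line with Protocol Appendix 4, which counts an increase in either. A rule based on grade alone would be narrower than the SAP's own notion of worsening.

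As a minor clarification, replace onset dates with onset date and time for Day 1 events where the time is recorded. Treat a Day 1 event with a missing time as treatment-emergent, which extends the existing conservative approach to partial dates. The imputation rule in SAP 9.5 works at the level of days and does not address a complete date without a time.

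The cost is one SAP sentence and one derivation flag, settled before database lock. It depends on the eCRF capturing worsening and, for Day 1, onset time. The documents do not state that it does, so this should be confirmed when the sentence is changed.

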15.1.1 All Adverse Events

Treatment-emergent AEs and participants experiencing TEAEs will be summarized by ethnic group and overall in tables with:

- The number and percentage of participants with any TEAE, any related TEAE, any serious TEAE, any related serious TEAE, any Grade ≥ 3 TEAE, any related Grade ≥ 3 TEAE, any AESIs, any TEAE leading to death, any related TEAE leading to death, any TEAE leading to study discontinuation
- The number and percentage of participants with at least one TEAE by SOC and PT, and the number of events by SOC and PT
- The number and percentage of participants with at least one TEAE and the number of events by grade, SOC, and PT
- The number and percentage of participants with at least one related TEAE and the number of events by SOC and PT
- The number and percentage of participants with at least one related TEAE and the number of events by grade, SOC, and PT

Unless otherwise stated, AEs will be displayed with SOC terms and PTs within each SOC term sorted alphabetically.

For determining incidence counts, within each level of TEAE term, if a participant experiences more than one occurrence, the participant will only be counted once for that TEAE.

Adverse events related to any study intervention are those events with relationship missing, unknown or related.

In case a participant had events with missing and non-missing severity, the maximum non-missing severity will be displayed.

15.1.2 Adverse Events Leading to Discontinuation of Study Intervention

Not applicable.

15.2 Deaths, Other Serious Adverse Events, and Other Significant Adverse Events

15.2.1 Deaths

A listing of deaths, if any, will be provided.

15.2.2 Serious Adverse Events

A listing of serious AEs (SAEs), if any, will be provided.

15.2.3 Other Significant Adverse Events

Not applicable.

15.3 Clinical Laboratory Evaluation

Listings and summary statistics at each assessment time will be presented using the Système International (SI) units. Normal ranges will be provided by the central laboratory, and out of range flags will be calculated based on the normal ranges. Laboratory data not transferred from the central laboratory in SI units will be converted to SI units before processing. Both original units and SI units will be provided in the SDTM domain.

Continuous clinical laboratory data (hematology, and biochemistry) will be summarized by ethnic group (Japanese, non-Japanese East Asian and overall) and time point using descriptive statistics for baseline (see definition in Section 9), each evaluation during the study, and change from baseline to each evaluation.

Box-and-whisker plots for the absolute change from baseline by ethnic group (Japanese, non-Japanese East Asian and overall) and time point will also be provided.

Listings of all clinical laboratory data for each participant will be provided, with values outside the normal ranges indicated. Listings of abnormal test results (low and high) will be provided.

15.4 Vital Signs

Vital signs data will be summarized by ethnic group (Japanese, non-Japanese East Asian and overall) and time point using descriptive statistics for baseline (see definition in Section 9), each evaluation during the study, and change from baseline to each evaluation. Listing of vital signs data will be provided.

15.5 Other Safety or Tolerability Evaluations

Safety ECG data will be summarized by ethnic group (Japanese, non-Japanese East Asian and overall) and time point using descriptive statistics for baseline (see definition in Section 9), each evaluation during the study, and change from baseline to each evaluation. Listing of safety ECG data will be provided.

A listing of meal details will be provided.

15.6 COVID-19 Impact

A listing of all participants affected by the COVID-19 related study disruption (e.g. AEs/SAEs, missed visit, missed dose, treatment/study discontinuation, protocol deviation including minor, screen failure, etc.) will be provided.

16 Analyses of Other Endpoints

16.1 Pharmacokinetics

PK evaluation will be performed by the Clinical PK/PD Group, Merck Healthcare KGaA, Darmstadt, Germany, or by a CRO selected by the Sponsor.

All descriptive summaries of PK data will be performed on the PK Analysis Set. All PK data will be descriptively summarized by ethnic group and overall.

16.1.1 Descriptive Statistics of PK Concentration Data

PK concentrations will be descriptively summarized using: number of non-missing observations (n), arithmetic mean (Mean), standard deviation (SD), coefficient of variation (CV%), minimum (Min), median (Median), maximum (Max).

Descriptive statistics will only be calculated for $n > 2$ in which a measurement of BLQ represents a valid measurement and will be taken as zero for summary statistics of PK concentration data. In case $n \leq 2$, individual data will be presented (min, max) in summary tables.

Descriptive statistics of PK concentration data will be calculated using values with the same precision as the source data and rounded for reporting purposes only. PK concentrations will be carried over with full precision as provided in the source data without any rounding applied to CDISC SDTM PC and ADaM PC domains.

The following conventions will be applied when reporting descriptive statistics of PK concentration data:

n:	0 decimal place
Mean, Min, Median, Max, SD:	3 significant digits
CV%:	1 decimal place

